8. ETHICAL CONSIDERATIONS

8.1 Regulation statement

The study will be conducted according to the principles of the Declaration of Helsinki (www.wma.net) and in accordance with the Medical Research Involving Human Subjects Act (WMO) and other guidelines, regulations and Acts.

The recruiter will explain the nature of the study and will inform the participant that participation is voluntary and that the participant can withdraw from the study at any time. Written informed consent will be obtained from each participant prior to any study procedure. A copy of the signed consent form will be given to every participant and the original will be maintained by the research team.

8.2 Recruitment and consent

General practice patient lists will be screened for potentially eligible participants (see section 4.2 and 4.3). The latter will be informed by their GP about the study. If they are interested in taking part their contact details will be given to the study team. Interested potential participants will be contacted by a member of the study team who will answer any questions they may have about the study and if they are still interested booked in for an inclusion visit. Recruitment procedures can be adapted to local circumstances and regulations.

Participants that report a pneumonia during the study, or have missing data concerning a medically-attended ARTI, are asked additional informed consent to perform a medical notes review. This notes review includes amongst others obtaining report of physical examination, performed scans (chest X-ray), blood testing (CRP/ESR), prescription of medication (such as antibiotics or respiratory medication) and clinical diagnoses made by the physician. A medical notes review will be performed only in these specific cases in order to obtain or validate this information which is key for the primary and secondary study outcomes.

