5.1.2 Secondary study parameters/endpoints

- The incidence rate of all-cause MA-ARTI or events leading to worsening of cardiorespiratory status. The incidence rate will also be summarized separately for outpatient events and for both inpatient and outpatient events combined through the RSV season of follow up. Subgroup analyses will summarize these endpoints by RSV season.
- 2. Mortality through the RSV season of follow up for RSV-associated deaths and all cause deaths.
- 3. Health care costs and resource use for RSV-associated and all-cause MA-ARTI (inpatient or outpatient) or events leading to worsening cardiorespiratory status with regard to hospital duration, incidence and duration of intensive care unit stay, supplemental oxygen use, antibiotic and antiviral use and number of outpatient visits (e.g., ER visit, physician office/outpatient visits) and HRQoL.
- The incidence rate of RSV-associated secondary bacterial pneumonia events (defined as pneumonia within 21 days after RSV infection) and associated antibiotic use will be summarized.
- 5. Change in frailty over the course of study.
- 6. Sample collection for biomarker analysis to investigate possible biomarkers which are predictive of severe or complicated RSV disease in older adults. With these

clinical samples a biobank will be established for identifying potential biomarkers of RSV disease severity for further validation.

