5.3 Study procedures

1. Inclusion Visit (August/September)

At the inclusion visit, after eligibility has been confirmed and fully informed consent completed, the following procedures will take place:

- A baseline questionnaire about, but not limited to, demographic data, medical history, risk factors for RSV disease and quality of life will be completed.
- A blood sample (60 ml) and a nasopharyngeal sample will be collected.
- 2. Throughout the RSV season (October 1st to May 1st, or longer if RSV is still circulating based on national viral surveillance programs):

Participants will be asked about respiratory symptoms during the RSV winter season by weekly contact by telephone (verbally or text message), email, telephone app or online questionnaire. If they experience an ARTI, participants are instructed to contact the study team. Two nasopharyngeal and one oropharyngeal sample will be collected by home visits (or in the doctor's office when preferred by participant) within 3 days after contact with the study team. One nasopharyngeal sample will be used for direct RSV RT-PCR testing. The other samples will be stored at -80°C. If RSV is positive a blood sample will be drawn (60 ml) and a nasopharyngeal sample will be collected and stored at -80°C. In addition, in case of a RSV ARTI, 1-2 weeks after onset of symptoms another blood sample (30ml) and nasopharyngeal sample will be collected. During the episode of respiratory disease, participants are asked to complete a diary on respiratory symptoms and HRQoL. At the end of the episode, participants are asked to complete a questionnaire on medical resource use, interruption of daily activities and HRQoL. If participants have been admitted to the hospital, a questionnaire about the reason for hospitalization, diagnosis and treatment will be completed by the study team using medical data from the admitted hospital.

- 3. At the end of the RSV Season (May/June)
 - A blood sample (60 ml) and a nasopharyngeal sample will be collected.
- 4. Approximately one year after inclusion (+/- 2 months).
 - A questionnaire about changes in living conditions, health status and quality of life will be completed.

 Table 2. Overview of sampling of older adults study.

Moment of	Sample	Volume	Analysis (minimum
sampling		00 1	amount)
At beginning of RSV	Serum (venous)	20 ml	RSV serology (350-400 μl)
season (Oct.)			Proteome (100 µl)*
	Paxgene (venous)	10 ml	Transcriptome (200 µI)*
	Whole blood	30 ml	DNA/GWAS (200 µl)

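### Outpatient pneumonia after RSV is checked against medical notes only in participants who report it or have missing attendance data, so this secondary endpoint is probably under-counted

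*Protocol*

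**What the plan says.** Section 8.2 sets two triggers for a notes review, both subject to extra consent: "Participants that report a pneumonia during the study, or have missing data concerning a medically-attended ARTI, are asked additional informed consent". It then limits the review: "A medical notes review will be performed only in these specific cases in order to obtain or validate this information". The same sentence describes the information as that "which is key for the primary and secondary study outcomes". What is retrieved goes beyond confirming a visit; it includes "prescription of medication (such as antibiotics or respiratory medication) and clinical diagnoses made by the physician", as well as imaging and blood results.

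Section 5.1.2 makes post-RSV pneumonia a secondary endpoint: "The incidence rate of RSV-associated secondary bacterial pneumonia events (defined as pneumonia within 21 days after RSV infection"; associated antibiotic use is summarised with it. Table 1 in section 2 lists its sources as hospital medical data, the diary and questionnaires.

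Section 5.3 separates inpatients from outpatients. For an admission, a form on reason, "diagnosis and treatment will be completed by the study team using medical data from the admitted hospital". For an outpatient, the source is the participant: "At the end of the episode, participants are asked to complete a questionnaire on medical resource use, interruption of daily activities and HRQoL". Episodes are detected actively: "Participants will be asked about respiratory symptoms during the RSV winter season by weekly contact by telephone" or by other media. Section 3 adds a questionnaire at about one year that asks again about respiratory disease.

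**The concern.** Pneumonia is a clinician's diagnosis. For an admitted participant the protocol obtains it from the hospital record. For an outpatient it looks in the record only if the participant has already reported a pneumonia, or if data on an attended ARTI are missing. A participant with confirmed RSV who saw the GP, was given antibiotics, returned complete forms and did not report pneumonia falls outside both triggers.

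The check is therefore uneven. A reported pneumonia can be confirmed or refuted; a complete report of no pneumonia stands as it is. At stake is the outpatient part of the post-RSV pneumonia rate. These events are a subset of a small number of RSV cases, so each missed one counts. The restriction governs data collection and consent, so a later analysis plan could not recover records that were never requested.

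**Working it through.** The protocol gives no figure for how well participants report pneumonia or attendance, how often data are missing, or how many consent to review. There is no stated figure to reproduce. The check below concerns direction only, and every input marked *assumed* is an illustration.

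**1. Outpatient pneumonia under the present triggers**

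Let T be the true outpatient pneumonias, Se the share that participants report, F the false reports, m the share of unreported cases reached through the missing-data trigger, and c the consent to review. Assume that the notes give the right answer, and that a report refuted by them is dropped.

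Counted = T·Se + T·(1 − Se)·m·c + F·(1 − c)

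With T = 10 and F = 2 (*assumed*):

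| Se | m = 0, c = 1 | m = 0.2, c = 1 | m = 0, c = 0.8 | m = 0.2, c = 0.8 |
|---|---|---|---|---|
| 0.9 | 9.0 | 9.2 | 9.4 | 9.56 |
| 0.8 | 8.0 | 8.4 | 8.4 | 8.72 |
| 0.7 | 7.0 | 7.6 | 7.4 | 7.88 |

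For example, at Se = 0.8, m = 0.2, c = 1: 8 + 2 × 0.2 + 0 = 8.4. All twelve entries lie below 10. The missing-data trigger adds cases but does not close the gap.

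The direction is not a certainty. The count falls short when F·(1 − c) is less than T·(1 − Se)·(1 − m·c). With full consent that holds whenever some cases go unreported and the missing-data trigger does not reach them all. With low consent, unreviewed false reports can offset the loss: at Se = 0.9, m = 0, c = 0.5 the count is 9 + 0 + 1 = 10.

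**2. Self-reported outpatient attendance (part of the primary endpoint)**

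A complete attendance report is not reviewed unless a pneumonia is reported, so both kinds of error stay in. With T true medically attended RSV cases, M RSV ARTIs without attendance, and Sp the share of those M correctly reported as unattended:

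Counted = T·Se + M·(1 − Sp)

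Section 4.4 gives 3.0% and about 1,000 participants, so T = 30. Se, Sp and M are *assumed*:

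- Sp = 1, Se = 0.95, 0.90, 0.80: 28.5, 27, 24 (2.85%, 2.7%, 2.4%)
- M = 30, Se = Sp = 0.90: 27 + 3 = 30, no net error
- M = 60, Se = Sp = 0.95: 28.5 + 3 = 31.5, upward
- M = 60, Se = Sp = 0.90: 27 + 6 = 33, upward

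The sign depends on unknown inputs. For scale, the exact 95% interval for 30 of 1,000 is 2.03% to 4.26%.

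**3. Pneumonia under the proposed trigger**

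Reviewing every confirmed RSV ARTI with a reported attendance or antibiotic course sets m = 1 for that group. If all T fall in it, full consent gives 10 at each Se. With c = 0.8:

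- Se = 0.9: 9 + 0.8 + 0.4 = 10.2
- Se = 0.8: 8 + 1.6 + 0.4 = 10.0
- Se = 0.7: 7 + 2.4 + 0.4 = 9.8

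Under the present rule with m = 0 and the same consent, the counts are 9.4, 8.4 and 7.4.

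**4. Workload**

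3.0% × 1,000 = 30. After the 10% loss to follow-up in section 4.4, 3.0% × 900 = 27.

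**The case against.** The strongest reply is that section 8.2 is not a check on positives alone. The missing-data trigger exists to obtain information as well as to validate it, and the notes carry diagnoses and prescriptions, so it can add a pneumonia that the participant never mentioned. This stands. A reader might infer that the review can only remove events; the text does not support that. The trigger does not, however, reach a form that is complete and wrong. Read literally, it also concerns an ARTI already known to be medically attended.

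A reader might also infer that the primary incidence of medically attended RSV is biased downwards. The documents do not support that either: over-reported attendance is mostly left unreviewed and can cancel or reverse the loss, as step 2 shows.

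Further, the questionnaires are not in the protocol and may ask directly about a doctor's diagnosis. Weekly contact, the diary, the end-of-episode questionnaire and the one-year questionnaire all narrow the gap. That too stands, but these are all self-report: they raise Se without supplying the clinician's finding. The protocol also states no rule for dropping a refuted report; that is inferred from the aim of validation.

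Nor does review necessarily move the count away from the truth. With 5 true events, sensitivity 90% and positive predictive value 60% (both assumed), raw self-report gives 5 × 0.9 / 0.6 = 7.5, and review of positives gives 4.5, which is closer to 5.

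Finally, limiting access to records in a low-burden observational study is a defensible choice, and no other section contradicts it. The point is a weakness of design, not an inconsistency.

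**Conclusion.** The point holds for one component of one secondary endpoint. Outpatient pneumonia after RSV is not sought in RSV-positive participants who have complete data, saw a clinician and did not report pneumonia, and the count is probably too low. The size cannot be computed from the documents. The 7.0 to 9.6 of 10 rests on assumed sensitivity of 70% to 90%, two false reports, 0% to 20% recovery through missing data and 80% to 100% consent. The direction also assumes that false reports left in by refused consent do not outweigh the missed cases.

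Admitted participants are not affected, because their data come from the hospital. Self-reported outpatient attendance is largely unvalidated, with an unknown direction of error, so nothing is claimed about bias in the primary endpoint. The change is a worthwhile, inexpensive improvement; the primary analysis does not depend on it.

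**What to change.** Amend section 8.2 so that consent for notes review is sought in every RT-PCR-confirmed RSV ARTI with any reported medical attendance or antibiotic course, whether or not the participant reports pneumonia. Keep the two existing triggers for other ARTIs. Base the outpatient part of the post-RSV pneumonia endpoint on the notes where consent is given, and report how many cases rest on self-report because consent was refused.

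The cost is a short amendment and about 27 to 30 reviews in total at the protocol's 3.0%, some of which the present triggers would already have prompted. The existing team can carry this; the downside is a few dozen more consent and record requests.

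The change does not detect a false report of no medical contact. That would need review of all RSV-positive ARTIs, attended or not, a number that the documents do not give.

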8.3 Benefits and risks assessment, group relatedness

 Nasopharyngeal swab: A small swab will be introduced deep into the nose and some mucus will be collected. The procedure can cause a brief moment of discomfort, however, the duration of this procedure is less than 10 seconds and the swab is very soft. Trained personnel will perform this. Minor complications (for example nose bleed) have been described, but are rare.

- Oropharyngeal swab: A small swab will be introduced into the mouth towards the
 oropharynx and some mucus of the oropharynx will be collected. This is a noninvasive technique. The procedure can cause a brief moment of discomfort, however,
 the duration of this procedure is less than 10 seconds and the swab is very soft.
 Trained personnel will perform this.
- Venipuncture: Drawing venous blood is moderately painful. Trained personnel will perform this. Minor complications like bruising have been described.

There is no clear clinical benefit for the participants taking part in this proposed study. However, the results of this study aim to support the understanding of the burden of RSV disease, which is important for the implication of future preventive and therapeutic interventions.

8.4 Compensation for injury

Due to the type of study, observational with non-invasive diagnostic procedures without major complications, as previously described, no serious adverse events are to be expected and participating in the study is with minimal risks. Therefore we request dispensation from the statutory obligation to provide insurance.

9. ADMINISTRATIVE ASPECTS, MONITORING AND PUBLICATION

9.1 Handling and storage of data and documents

Full data management will be performed by Julius Center. Data will be stored in a cloud-based database. Data will be anonymized before they enter the database. Each participant will receive a unique identification number, which cannot directly be traced back to the participant. The study team will keep a participant identification code list to trace data to an individual participant, if necessary. Data will be kept for at least 15 years. The handling of personal data will be in compliance to local regulations.

Data management of this study will be performed by a professional and experienced data management team. This team will coordinate and implement a high quality IT-infrastructure that will be necessary for the collection, controlling and reporting of the research data of this study.

A GCP compliant electronic data capture (EDC) system will be used to guarantee a correct, complete and consistent data collection. Web-based case report forms will be developed and implemented on the EDC system. By using comprehensive data validation checks within these forms, only data of high quality can be submitted to the study database. The forms, integrated into the EDC system, can easily be accessed by a standard web browser.

The data management system facilitates the collection of data, supports the monitoring processes and provides real time progress reports for management of the study. After last patient out, the database can rapidly be closed and data made available for further analysis and publication purposes.

The system meets all GCP guidelines for electronic data collection in terms of protecting data integrity and securing the information collected. This means, among other things, that users will get a role based access to the system after they have logged-in using their own username and password. The system will log all data entry steps with timestamps, update reasons and user information. The role based access to the system will avoid unauthorised data access and prevents that users perform actions that they are not allowed to do. Data from the EDC system will be transferred over the internet using secured data communication protocols. Data will be stored automatically and regularly back-ups will make sure that data never will be lost. Databases and web servers will be hosted in data centers that meet the highest possible security requirements.

9.2 Monitoring and Quality Assurance

Monitoring of the conduct of the study will be performed according to GCP guidelines at initiation and once yearly for the duration of the study. Monitoring is explained in more detail in the site specific separate monitoring plan.

9.3 Amendments

Amendments are changes made to the research protocol after a favourable opinion by the accredited METC has been given. All amendments will be notified to the METC that gave a favourable opinion. All substantial amendments will be notified to the METC. Non-substantial amendments will not be notified to the accredited METC, but will be recorded and filed by the sponsor.

9.4 Annual progress report

The sponsor/investigator will submit a summary of the progress of the trial to the accredited METC once a year. Information will be provided on the date of inclusion of the first subject, numbers of subjects included and numbers of subjects that have completed the trial, serious adverse events, other problems, and amendments.

9.5 Temporary halt and prematurely end of study report

The sponsor will notify the METC immediately of a temporary halt of the study, including the reason of such an action.

In case the study is ended prematurely, the sponsor will notify the accredited METC within 15 days, including the reasons for the premature termination.

Within one year after the end of the study, the investigator/sponsor will submit a final study report with the results of the study, including any publications/abstracts of the study, to the accredited METC.

9.6 End of the study

The investigator/sponsor will notify the accredited METC of the end of the study within a period of 8 weeks. The end of the study is defined as the moment that the last included participant has been followed up for 12 months.

9.7 Public disclosure and publication policy

Results of this research are disclosed unreservedly.

Managing an organisation like RESCEU can be challenging due to the size of the project, its ambition, the variety of activities and their interdependencies. The project aims to harmonise the interests of the public and EFPIA partners. Therefore, a strong internal trust and communication interface is crucial to setting the project up for success.

The project is composed of complementary, as well as parallel activities, with strong interdependencies between critical work packages outputs. This will require the need for a detailed time schedule for many of the tasks, which will need close monitoring and communication between team members to avoid bottlenecks and to allow effective progress of deliverables.

The management structure needs to be a balance between a simplistic standard scheme (which will not be able to address the needs of a project of this level of complexity) and an excessive super-structure (that would impose a cumbersome bureaucracy to the project and thus impede its scientific and technical progress).

Taking into account these project characteristics, the management structure proposed for RESCEU is based on a multi-level organisation that balances:

[figure not shown]
- The fulfilment of the work plan per se.
- The management of trade-offs affecting scope, quality, time and cost.
- The primary focus needed on critical activities that aim to ensure the achievement of milestones and that contribute to strategic objectives.
- The relationships and trust amongst partners, including conflict resolution.
- The quality and efficiency with which the project activities are carried out.
- The appropriate implementation of the Consortium Agreement, with careful attention to the governance procedures, intellectual property policy and the related use of results.
- The implementation of the Grant Agreement, including administrative and financial elements.
- The creation and management of a wider scientific forum encompassing interested organisations beyond the project partnership (Associate Partners).

Taking into account the above, a management structure has been designed with the following components included:

• **RESCEU Forum (RF)**: forum for discussion, dissemination and scientific community-building within the project. The RF will consist of the project partners (Beneficiaries)

- and the Associate Partners and may be convened by electronic means or face-to-face with the purpose of stimulating discussion and promoting dialogue on scientific issues. The RF will not have decision-making powers.
- General Assembly (GA): body composed of all Beneficiaries participating in the
 project, with the ultimate decision-making responsibility in matters affecting the overall
 project strategy and composition of the consortium. The GA will meet annually and
 will adopt decisions by majority each partner having a vote-, except in cases were
 unanimity is required according to IMI rules.
- Steering Committee (SC): leadership team with 50/50 vote allocation between EFPIA/non-EFPIA members, composed of WP (Co-) Leads (from academia and EFPIA) or their designated representatives. The SC is responsible for decision making on most issues related to project execution, technical development decisions, work plan updates, and effort/budget re-assignment in order to pursue optimal efficiency. Meetings will take place regularly, typically every two months. The attendance of one representative from each WP will be required for quorum. Decisions will be determined by majority vote of attendees.
- Operations Team (OT): executive group composed of the Coordinator, the Project Leader and the Project Manager (but not restricted to those), responsible for the dayto-day operational and technical aspects of the project. The OT will meet frequently (i.e. bi-weekly by teleconference) to monitor the project progress and to address any issues that may arise.
- Project Management Office (PMO): team dealing with the day-to-day management of the project. Regular meetings, mostly by teleconference, will be established to appropriately follow up on management matters.
- **Task Forces**: Result-oriented ad-hoc teams will be created as needed, with a clear and exclusive mission of studying/resolving any issues between WPs.
- Advisory Boards: consultative bodies for ethical, scientific and technical matters.
 RESCEU intends to establish three advisory boards formed by external experts: the International Scientific Advisory Group (ISAG), the RESCEU Ethics Advisory Committee (EAC) and the RESCEU Patient Advisory Board (PAB).

Figure 3. Governance structures in RESCEU.

12. APPENDIX 2: Glossary of Terms

According-To-Protocol (ATP) cohort: This cohort will include all cases enrolled in the study who meet the criteria defined in the protocol for the considered analysis.

Acute respiratory tract infection (ARTI): symptoms of an upper and/or lower respiratory tract infection, such as runny or blocked nose, coughing, fast breathing, chest indrawing, shortness of breath, low oxygen saturation.

Cohort study: A form of epidemiological study where subjects in a study population are classified according to their exposure status/disease and followed over time (prospective/retrospective) to ascertain the outcome(s).

Epidemiological study: An observational or interventional study without administration of medicinal product(s) as described in a research protocol.

Evaluable: Meeting all eligibility criteria, complying with the procedures defined in the protocol, and, therefore, included in the According-To-Protocol (ATP) analysis (see Section 9.3 for details on criteria for evaluability).

Health Burden: Burden of the disease imposed on the study population in terms of incidence of the disease and associated healthcare utilization in any healthcare setting.

Healthcare settings (Healthcare Utilization): Primary, secondary and tertiary care settings such as self-care with over-the-counter [OTC] drugs, general practitioner (GP) visits, emergency room (ER) visits, hospital visits, etc.

Interventional Human Subject Research:

Studies in which participants are administered medical care, medicinal products and/or medical/scientific procedures as described in a research protocol.

Lost-to-Follow-up is defined as no contact by the subject's parent(s)/LAR(s) over the period of 3 planned contacts and/or 2 months and after a final attempt has been made by mail. Once this has been reached, the subject is censored at the time of last contact.

Sponsor: The sponsor is the party that commissions the organisation or performance of the research, for example a pharmaceutical company, academic hospital, scientific organisation or investigator. A party that provides funding for a study but does not commission it is not regarded as the sponsor, but referred to as a subsidising party.

Prospective study: A study in which the subjects/cases are identified and then followed forward in time in order to address one or more study objectives.

Research protocol: A document that describes the objective(s), design, methodology, statistical considerations, and organization of a study. The protocol usually also gives the background and rationale for the study, but these could be provided in other protocol referenced documents.

Seroprevalence: The total number of cases within the study population at a specific time that test positive for the disease based on blood serum specimens.

Study population: Sample of population of interest.

Sub-cohort: A subgroup of the total cohort of study participants for whom the planned study procedures are different from those planned for the other study participants.

Participant: Term used throughout the protocol to denote an individual who has been contacted in order to participate or participates in the epidemiological study or a person about whom some medical information has been recorded in a database.

Participant number: A unique number identifying a subject, assigned to each participant consenting to participate in the study.

Surveillance: The ongoing systematic collection, collation, analysis, and interpretation of descriptive epidemiological health data on a specific disease. Surveillance can monitor incidence and/or prevalence, and/or inform about when and where health problems are occurring and who is affected.

13. APPENDIX 3: Clarification of exclusion criteria based on immunosuppression

Exclusion criteria based on immunosuppression related exclusion criteria are as follows:

- Exclusionary immunosuppressive conditions: "Any known or suspected immunosuppressive condition, acquired or congenital, as determined by history and/or physical examination."
- Exclusionary immunosuppressive medications: "Chronic administration (defined as more than 14 continuous days) of immunosuppressants or other immune-modifying drugs within 6 months prior to study participation. The use of topical, inhaled, and nasal glucocorticoids will be permitted."

Below is a non-exhaustive list of immunosuppressive conditions and immunosuppressive medications/therapies that are exclusionary according to above two exclusion criteria:

- A) Potential subjects with HIV infection, regardless of whether the subject is receiving anti-retroviral treatment.
- B) Potential subjects with congenital immunodeficiencies.
- C) Potential subjects with active leukemia, lymphoma, or other hematologic malignancy according to following criteria:
 - i. Disease known to be present and active (previously treated patients with no evidence of active disease in the previous 6 months are acceptable, provided they meet the requirements for no ongoing cytotoxic drug therapy).
 - ii. With or without ongoing therapy.
- D) Potential subjects with any prior history of hematopoietic stem cell transplantation.
- E) Potential subjects with certain medical conditions (for example, but not limited to, solid tumors/malignancies, or solid organ transplant recipients) requiring any of the following ongoing:
 - i. Cytotoxic drug therapy ongoing or within 6 months prior to study participation
 - ii. Systemic glucocorticoids in excess of the limits of the protocol (≥10mg of prednisone per day or equivalent for more than 14 continuous days within 6 months prior to study participation)
 - iii. Chronic immunosuppressant therapies ongoing or within 1 month prior to study participation to manage solid organ transplants: Calcineurin Inhibitors (e.g. Tacrolimus and Cyclosporine), Antiproliferative agents (e.g. Mycophenolate Mofetil, Mycophenolate Sodium and Azathioprine), mTOR inhibitor (e.g. Sirolimus, Tacrolimus), and/or steroids (e.g. prednisone)
- F) Potential subjects with end-stage renal failure or hepatic failure

The following potential subjects should NOT be excluded from participation:

1) Potential subjects with known or suspected "autoimmune diseases" who are untreated or treated with immunomodulatory monoclonal antibodies/biologicals and who have NOT had opportunistic infections.
